8. EFFICACY ASSESSMENTS

Change from baseline to 24 hours after infusion start in the E/Ea ratio assessed by tissue Doppler will be assessed as primary end-point. Other echocardiographic parameters (LVEF, LV end diastolic and end systolic volumes, SVI, E/A ratio, other Tissue Doppler parameters such as Sa, Da and Aa) will be assessed as secondary end-points. These parameters will be assessed also at 48 hours as further exploratory analyses.

Dyspnoea will be assessed at baseline using a 100 mm VAS scale. Further assessments will be repeated at 3, 6, 12, 24 and 48 hours after the start of drug infusion only in patients presenting dyspnoea at baseline.

NT-proBNP will be measured by the local laboratory only for evaluation and screening inclusion. While at baseline, at 24 hours after infusion start (day 2), on Day 3, at day 4 or at discharge) and at day 30, NT-proBNP will be measured by the central laboratory

Episodes of worsening HF, defined by the need to increase the dose or reinitiate i.v. therapy with diuretics and/ or other inotropic agents during the hospitalization, will be recorded.

9. SAFETY ASSESSMENTS

- 1. AEs will be monitored throughout the study (i.e. from the time of signature of informed consent to treatment end + 30 days);
- 2. Physical examination (HF signs included) at screening, baseline, on study Day 4 or at discharge, and on study Day 30 during the follow up visit;
- 3. Vital signs (HR, BP, respiratory rate, body temperature and dyspnoea)) will be measured at screening, (concomitantly to hemodynamic measurements) during the pretreatment period, at 3, 6, 12, and 24 hours after infusion start, and then on study Day 3 and Day 4 or at discharge, and on study Day 30 during the follow up visit;
- 4. 12-lead ECG (HR, RR and PR intervals, QRS duration, QTc, rhythm, ectopy, ischemic changes) will be recorded and locally analyzed at screening and on study Day1, Day2, Day 3 and Day 4 or at discharge, and on study Day 30 during the follow up visit;
- 5. Continuous Holter monitoring will take place during screening, treatment (Day 1), and Day 2.
- 6. Blood samples will be collected and sent to the local laboratory during screening, 48 hours after infusion starts and on Day 30 to measure the following safety parameters:

Protocol N°: CVT-CV-002 42

- a) Hematology: red blood cell (RBC) count, Hb, hematocrit (Hct), white blood cell (WBC) count, differential WBC count, platelet count;
- b) Blood chemistry: electrolytes (Na⁺, K⁺, Ca⁺⁺, Cl⁻), albumin, total protein, glucose, creatinine, eGFR, BUN (blood urea nitrogen), alkaline phosphatase, ALAT, ASAT, total and conjugated bilirubin, gamma glutamyl transferase (γ-GT), total cholesterol, triglycerides;
- 7. Blood samples for creatinine will be collected by the local laboratory at each time after infusion start
- 8. cTnT or cTnI will be measured locally during screening. While cTnT only will be measured by the central laboratory, at pre-dose in two samples, at 3, 6, 12, 24, 48, 72 hours after infusion start or at discharge and at 30days by using the hs test from Roche cobas. Incidence of cTnT elevation (>50% or > 20% relative increase over the basal cTnT levels at baseline, for patients with cTnT levels at baseline < or ≥ of the 99% URL (upper reference levels, as defined for the Roche hs test, in patients with normal renal function, eGFR ≥85 ml/min); in patients with eGFR below this value, the renal function variations must be considered in evaluating the significance of the cTnT changes).

10. REPORTING OF ADVERSE EVENTS

10.1 Definition of Adverse Event (AE)

Adverse event (AE) is an adverse medical event that occurs following informed consent signature, the event is not necessarily related to the treatment. Therefore, adverse events may be any discomfort and unconscious signs (such as abnormal laboratory examination results), symptoms or illnesses.

- Any adverse event, whether serious or not, whether related to the treatment or not, should be recorded on the CRF.
- Investigator should follow up the patients that dropped out because of any adverse event until recovery, and record the date of AE occurring and recovering.
- If during adverse event follow-up, the adverse event progresses to an "SAE", or if a subject experiences a new SAE whose relationship to the study drug(s) cannot be ruled out, the investigator must immediately report the information to the sponsor.

Protocol N°: CVT-CV-002

Even if the subject does not return to normal or to his or her previous state, the follow-up can be considered finished when the following procedures have been taken:

- The investigator judges that the follow-up of the subject concerned is no longer necessary based on the progress made during the follow-up,
- The reason for such a judgment is entered as a comment on the case report form for the follow-up.

10.2 Definition of Serious Adverse Event (SAE)

'Serious adverse event' is an event that induces hospitalization, prolonging the length of hospitalization, disability, affecting work ability, imperiling life or death, and congenital malformation.

- (1) SAE is one of the following situations:
 - That causes death
 - Teratogenesis, carcinogenesis or birth defect
 - That is dangerous to life and could induce permanent or remarkable disability
 - That induces permanent injury in organ function
 - That induces hospitalization or prolongs the length of hospitalization

(2) Hospitalization

According to the clinical study reports, the adverse events leading to hospitalization or prolongs the length of hospitalization will be regarded as serious adverse event (SAE). Including: hospitalized in a healthcare facility for the first time (even less than 24 hours) and the hospital transferred to the emergency/intensive care ward.

The hospitalization does not include the following institutions:

- rehabilitation institutions;
- asylum;
- occasional care service;
- nursing institution;
- sanatorium;
- routine hospitalization;

- (3) Hospitalization or prolonging the length of hospitalization without emergency clinical adverse event does not belong to SAE. For example:
 - hospitalization because of previous disease, which is unrelated to adverse event and with no worsening (e.g. examinations for the continuous abnormalities in laboratory tests prior to treatment);
 - for social reasons (such as homelessness);
 - for management reasons (such as routine health examinations per year or for convenience of drug administration);
 - hospitalization assigned or permitted by the protocol during the trial;
 - voluntary hospitalization unrelated to AE (such as selective plastic surgery);
 - Scheduled treatment or surgery for the whole protocol and/or subject's benefit, which is recorded at baseline;
 - Just for infusion of blood products.

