# Serious adverse event (SAE)

A SAE is an AE judged as serious.

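### Protocol 10.2 defines a serious adverse event twice: the lead sentence makes danger to life enough on its own, but the list names it only jointly with potential disability

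*Protocol*

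**What the plan says.** Protocol 10.2 opens with a one-sentence definition. An SAE is "an event that induces hospitalization, prolonging the length of hospitalization, disability, affecting work ability, imperiling life or death, and congenital malformation". Here disability and danger to life are separate entries in a series.

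A list follows, headed "SAE is one of the following situations", so each bullet is a sufficient criterion. It has five bullets: death; teratogenesis, carcinogenesis or birth defect; the combined bullet "That is dangerous to life and could induce permanent or remarkable disability"; permanent injury to organ function; and "That induces hospitalization or prolongs the length of hospitalization".

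Part (2) of the section widens the hospitalization ground to include "the hospital transferred to the emergency/intensive care ward". Part (3) narrows it: among the stays that do not count is "hospitalization assigned or permitted by the protocol during the trial".

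The SAP sets no criteria of its own. Its section 6.4 says "A SAE is an AE judged as serious", and section 7.8 tabulates SAEs by treatment group on that basis.

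**The concern.** The same event can be serious under the lead sentence and not serious under the list, and nothing in the section says which prevails. An investigator who works down the bullets may reach a different answer from one who works from the opening sentence.

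The inpatient setting makes this matter more than it would in an outpatient trial. Patients are already in hospital at inclusion (Protocol section 4), so a new admission cannot pick up an event that happens on the ward during the infusion. The relevant type of event is also foreseeable: Protocol 1.1 names atrial and ventricular arrhythmias as a hazard of conventional inotropes, and Protocol 1.2 says that the risk of infusing beyond six hours still has to be studied. This trial infuses for 24 hours.

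Several things depend on the seriousness judgement. Protocol 10.1 ties immediate reporting to the sponsor to SAE status. Protocol 5.4 describes the emergency envelope as prepared for SAEs, and one of the two unblinding statements in Protocol 5.2 limits code breaks to unexpected serious events. The SAP's SAE tables take the judgement as given.

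**Working it through.** No arithmetic applies, so the check sets the two definitions in Protocol 10.2 side by side and classifies one test event under each.

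| Ground | Lead sentence | List |
|---|---|---|
| Death | yes | yes, own bullet |
| Danger to life alone | yes | no bullet |
| Disability alone | yes | no bullet |
| Danger to life together with potential disability | yes (either part is enough) | yes, combined bullet |
| Permanent organ injury | not named | yes, own bullet |
| Admission or longer stay | yes | yes, own bullet |
| Birth defect or malformation | yes | yes, own bullet |

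**Test event.** An inpatient has a life-threatening ventricular arrhythmia during the infusion. It is reversed on the same ward and leaves no lasting harm.

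1. *Lead sentence.* The event endangered life. It is serious with no further condition.
2. *Bullet on death.* Not met.
3. *Bullet on teratogenesis, carcinogenesis or birth defect.* Not met.
4. *Combined bullet.* The first half is met. The second half asks whether the event could induce disability, so potential is enough. If the investigator sees that potential, the bullet is met and the definitions agree. If not, a literal reading fails.
5. *Bullet on permanent organ injury.* Not met.
6. *Bullet on hospitalization.* Met if the stay is prolonged or, through part (2), if the patient is moved to emergency or intensive care. The index admission itself does not count, because part (3) excludes stays that the protocol provides for. An early event that is quickly reversed need not lengthen a stay: SAP 6.3 counts every stay as 4 days plus any days after Day 4. That formula defines an efficacy variable and is not a seriousness rule.

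**Result.** The definitions disagree only when all four of these hold for a survived life-threatening event: no potential for lasting disability in the investigator's judgement; no permanent organ injury; no longer stay; no emergency or intensive care transfer.

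**What is kept in any case.** Protocol 10.1 has every adverse event entered on the CRF, serious or not. Protocol 6.2 has a separate endpoint for significant arrhythmias on continuous ECG, although Protocol section 9 limits Holter recording to screening, Day 1 and Day 2. SAP 7.8 also tabulates events leading to discontinuation. None of these routes gives an event SAE status.

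**The case against.** The strongest reply is that the bullet is loose English and sets no joint test. The section uses the same conjunction for alternatives elsewhere: the lead sentence ends "affecting work ability, imperiling life or death, and congenital malformation", and nobody takes malformation as a joint requirement. Part (2) likewise links first admission and ward transfer, which are plainly separate grounds. On that reading the bullet groups two grounds, and the definitions agree.

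A second reply is that the lead sentence already settles the test event. The list does not say that it is exhaustive, and nothing ranks it above the sentence that it follows. The CRF seriousness boxes are not in the documents, so it is unknown which wording they use.

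A third is that little is lost. The event stays in the adverse event data, the one interim analysis described concerns troponin (Protocol 14.2 and 16.3), and no stopping rule uses an SAE count.

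Much of this stands. A reader might infer that the protocol demands actual disability before a life-threatening event is serious. It does not: potential disability is enough even on the strict reading. A reader might also infer that the list is the operative checklist and overrides the lead sentence. No text says so. It would also go too far to say that such events vanish from the analysis.

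The replies do not remove the inconsistency. If the bullet can be read either way and nothing gives precedence, two investigators can follow the protocol and classify the same event differently. The absence of a numerical SAE stopping rule does not make the label idle either, since Protocol section 3 rests escalation to the second cohort on the safety board's evaluation of safety data.

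**Conclusion.** The concern holds as an internal contradiction in an operative safety definition. Its reach is limited to survived life-threatening events that meet all four conditions in the working, and only where the list is read literally. For those events the SAE classification, the immediate report to the sponsor and the entry in the SAP's SAE tables are at risk. The record of the event is not.

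The size cannot be derived, because the documents give no rate for such events. For scale only, each dose group has 40 patients, so one reclassified patient moves that group's SAE incidence by 1/40 = 2.5 percentage points if the patient has no other SAE. That is not an estimate of how many would be affected.

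The conclusion assumes that no other text resolves the conflict. Protocol 10.5, on SAE reporting, was not available in the text reviewed and could contain such wording. The CRF could too.

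**What to change.** Reconcile the list in Protocol 10.2 with the section's own lead sentence by splitting the combined bullet into two, one for danger to life and one for lasting or marked disability, so that either alone makes an event serious. Use the same wording in the CRF seriousness guidance, and check that section 10.5 agrees with it.

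If enrolment has ended, add an item to the blind data review that the SAP already plans before unblinding (sections 5.6 and 7.1): compare recorded adverse events with the reconciled definition, and query the investigator where an event appears to have endangered life but was not marked serious. Doing this before the treatment code is opened keeps reclassification independent of treatment group.

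The cost is a short text correction, a CRF guidance note and possibly a few more SAE reports. The analysis methods do not change.

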10.3 Relativity assessment of AE and Study Drug

Relativity between AE and test drugs is assessed by investigator according to the following:

1) Certainly related

Evidence of having taken test drugs; time sequence of AE happening and taking the drugs is credible; more rational to explain for AE with test drugs than other reasons; positive withdrawal reaction; positive repetition medication test; AE pattern accords with the past understanding of such drug or this kind of drugs.

2) Possibly related

Evidence of having taken test drugs; time sequence of AE happening and taking the drugs is credible; AE may be induced by the test drugs, or other reasons; positive withdrawal reaction.

3) Possibly unrelated

Evidence of having taken test drugs; AE is more likely to be induced by other reasons; negative or equivocal withdrawal reaction; negative or equivocal repetition medication test.

4) Certainly unrelated

The patient has not taken test drugs; or time sequence of AE happening and taking the drugs is incredible; or AE is induced by other notable reasons.

5) Uncertain

10.4 Severity assessment of Adverse Event

The strength or the serious degree of the adverse events can be divided into levels:

Mild: mild discomfort, no significant impact on daily life (work and study);

Moderate: moderate discomfort and impact on daily life, patients self-conscious symptom obvious, but can stand, no need to stop medicine

Severe: severe discomfort, significant impact on daily life, need for staying in bed, patients self-conscious symptom obvious is remarkable, and cannot stand, so need to stop medicine

10.6 Reporting of Pregnancy

If a woman becomes pregnant during the study period until Day 30, the investigator should report the information to the sponsor as if it is an SAE. The expected date of delivery or expected date of the end of the pregnancy, last menstruation, estimated fertility date, pregnancy result and neonatal data etc., should be included in this information.

The investigator will follow the medical status of the mother, as well as the fetus, as if the pregnancy is an SAE and will report the outcome to the sponsor.

When the outcome of the pregnancy falls under the criteria for SAEs [spontaneous abortion, induced abortion, stillbirth, death of newborn, congenital anomaly (including anomaly in a miscarried fetus)], the investigator should respond in accordance with the report procedure for SAEs. Additional information regarding the outcome of a pregnancy (which is categorized as an SAE) is mentioned below.

- "Spontaneous abortion" includes abortion and missed abortion.
- Death of an infant within 1 month after birth should be reported as an SAE regardless of its relationship with the study drug.
- If an infant dies more than 1 month after the birth, it should be reported if a relationship between the death and intrauterine exposure to the study drug is judged as "possible" by the investigator.
- In the case of a delivery of a living newborn, the "normality" of the infant is evaluated at the birth.

"Normality" of the miscarried fetus is evaluated by visual examination unless test results which indicate a congenital anomaly are obtained prior to miscarriage.

11. ADVERSE DRUG REACTION (ADR)

11.1 Definition of ADR

Harm reaction which unrelated to the purpose of treatment with the use of given medications at a normal dosage.

11.2 Reporting and monitoring of ADR

Reporting and monitor ADR is the process of finding, reporting, evaluating and controlling the adverse drug reaction.

12. PHARMACOKINETIC ASSESSMENT

Plasma concentrations of istaroxime and its metabolites PST2915, PST2922, and PST3093 will

be measured by liquid chromatography coupled to mass spectrometry (LC/MS/MS). When applicable, E and Z isomers will be measured separately.

In a subset of patients, a blood sample will be collected during the study period. In addition, a full PK profile will be established in a subset of Italian patients and in a subset of Chinese patients (to have 16 patients with istaroxime 0.5 μ g/kg/min and 8 patients with istaroxime 1.0 μ g/kg/min 24 total patients).

Blood will be sampled at the following time-points: 0 hour (pre-dose); 0.5, 3, 6, 12, and 24 hours after infusion start; 0.25, 0.5, 1, 4, 12, 24 hours after infusion end.

In the same subset of patients, concentrations of istaroxime and its metabolites will be measured by LC/MS/MS in urine collected from pre-dose to 48 hours after infusion end (3 collections will be scheduled: the first from pre-dose to 24 hours after investigational product infusion start, the second at 48 hours after infusion start, and the third at 72 hours after infusion start).

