
Globally, istaroxime was well tolerated and safe up to 1.5 μg/kg/min in patients suffering from acute HF. Doses above 1.5 μg/kg/min were not completely tolerated due to *Protocol N°: CVT-CV-002*

gastrointestinal disorders and infusion site pain.

In conclusion, in this study the lowest tested dose of $0.5 \mu g/kg/min$ of istaroxime infused for 6 hours produces a significant PWCP improvement over placebo, being the istaroxime safety profile satisfactory even at higher dose, in this setting.

Pharmacokinetic results showed that istaroxime levels increased proportionally in plasma reaching steady state concentration within the 1hour infusion. Estimated half-life for istaroxime was about 10 to 20 minutes at infusion rates higher than 1.66 μ g/kg/min. For rates of infusion lower than 1.66 μ g/kg/min, concentration dropped below the limit of quantification (10 ng/ml) at 5 min after stopping of the infusion.

The systemic exposure to istaroxime resulted to be linearly related to the administered dose [20]. A very high clearance was shown, resulting around 4500 ml/min for a 70 kg body weight man. The concentration of PST 2915, the main metabolite (6β-alcholol) of the parent compound, was also measured, showing that its concentration slowly increased during infusion period, reaching a maximum concentration within 10 min after the stop of the intravenous infusion of istaroxime [20]. The metabolite maximum concentration resulted to be about one half of the corresponding C_{max} of istaroxime. Half-life of PST 2915 resulted to be around 3 to 4.5 hours [20]. PST 2915 resulted to be an active metabolite showing the same stimulatory activity on SERCA2a of istaroxime but about 10 time less inhibitory activity on Na-KATPase and potency in in vivo animal models than istaroxime [20].

For infusion longer than 1 hour, PST 2915 plasma concentrations increase with time, while those of istaroxime remain at steady state, being constant the rate of infusion.

To evaluate the risk of a prolongation of istaroxime intravenous infusion over six hours, pharmacokinetic, efficacy and tolerability clinical studies have to be carried out. The above clinical evidence indicates that istaroxime could be a future treatment option for patients with ADHF and a low cardiac output state.

More detailed clinical information can be found in the Investigator's Drug Brochure [20].

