6.3 PK Parameters

After infusion, the following PK parameters will be measured and/or calculated for plasma E and Z isomers (when applicable) of istaroxime and its metabolites PST2915, PST2922, and PST3093, using the validated software WinNonLin® 5.2 or higher (Pharsight Corporation):

C_{max}: Maximum plasma concentration achieved after single dose

 t_{max} : Time to achieve C_{max}

AUC_{0-t}: Area under the concentration curve from administration to the last observed

concentration time t, calculated after single dose with the linear trapezoidal

method

 $AUC_{0-\infty}$: Area under the concentration/time curve extrapolated to infinity, calculated, if

feasible, as $AUC_{0-t} + C_t/\lambda_z$, where C_t is the last measurable drug concentration

 λ_z : Terminal elimination rate constant, calculated after single dose, if feasible, by

log-linear regression using at least 3 points

 $t_{1/2}$: Half-life, calculated, if feasible, as $ln2/\lambda_z$

MRT: Mean Residence time, calculated, if feasible, as AUMC_{0-\infty} / AUC_{0-\infty} - $t_i/2$,

where AUMC_{0-∞} is the area under the moment curve extrapolated to infinity

and t_i is the infusion duration

Cl_T: Total Body Clearance, calculated, if feasible, as Dose / AUC_{0-∞}

 V_z : Volume of distribution of the terminal phase calculated, if feasible as

Dose / (AUC_{0-\infty} x λ_z)

 V_{ss} : Volume of distribution at steady state calculated, if feasible as

(Dose x AUMC_{0- ∞}) / AUC_{0- ∞}²

The quality of log-linear regression (and, consequently, the reliability of the extrapolated PK parameters) should be demonstrated by a correlation coefficient $R^2 > 0.8$.

After infusion, the following PK parameters will be measured and/or calculated for urine E and Z isomers (when applicable) of istaroxime and its metabolites PST2915, PST2922, and PST3093, using the validated software WinNonLin® 5.2 or higher (Pharsight Corporation):

A_e: Total amount of analyte excreted in urine

A_e%: Percentage of analyte excreted in urine

Cl_R: Renal Clearance calculated, if feasible as A_e / AUC_{0-∞} (for istaroxime only)

These endpoints will be addressed in all the Italian patients and in a subset of Chinese patients.

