Data below the lower quantification limit (LQL) will be considered as 0 in the calculations and presented as BLQL in listings and tables. As a consequence of BLQL (i.e. 0) values, calculated geometric means (if requested) could be null. For this reason, in the presence of any null value, the geometric mean will be reported as not calculated (NC).

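### Istaroxime half-life, clearance and volume endpoints are at risk unless the trial's unstated assay limit lies far below the only limit the protocol gives

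*Protocol*

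**What the plan says.** Protocol section 2 makes the pharmacokinetics of istaroxime a study objective.

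- **Sampling.** Protocol section 12 draws blood at pre-dose, at 0.5, 3, 6, 12 and 24 hours after infusion start, and then at "0.25, 0.5, 1, 4, 12, 24 hours after infusion end". Section 7 adds a sample 48 hours after the end. The first post-infusion sample is therefore at 15 minutes.
- **Definitions.** Section 6.3 estimates the terminal rate constant λz by "log-linear regression using at least 3 points". Half-life and AUC0-∞ are computed from λz. Clearance is "Total Body Clearance, calculated, if feasible, as Dose" over AUC0-∞, and Cl_R, MRT, V_z and V_ss also use AUC0-∞. Each of these carries the qualifier *if feasible*; Cmax and AUC0-t do not.
- **Low values.** The same section states: "Data below the lower quantification limit (LQL) will be considered as 0 in the calculations".
- **Earlier experience.** Section 1.2 reports for the parent drug: "A very high clearance was shown, resulting around 4500 ml/min for a 70 kg body weight man". It also says: "Estimated half-life for istaroxime was about 10 to 20 minutes at infusion rates higher than 1.66" µg/kg/min. For lower rates, "concentration dropped below the limit of quantification (10 ng/ml) at 5 min after stopping of the infusion".
- **This trial's assay.** Section 12 names LC/MS/MS, with E and Z isomers measured separately when applicable. No quantification limit is given.
- **SAP.** The PK list in SAP 3.2 names λz, half-life, Cl_T, MRT, V_ss and V_z for the parent without a feasibility condition. SAP 7.9 plans no other analysis.

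**The concern.** Both study doses, 0.5 and 1.0 µg/kg/min, are below the 1.66 µg/kg/min under which section 1.2 says parent drug was already unquantifiable five minutes after the stop. The schedule then waits 15 minutes, and most of its later times suit the metabolite PST2915 (half-life around 3 to 4.5 hours) better than the parent. Nothing in sections 6.3 or 12 reconciles the two, and no assay limit is specified that would.

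Two things are at stake. The first is every parent parameter that runs through λz or AUC0-∞. If the assay limit is only moderately better than before, λz can be fitted in patients who eliminate slowly and not in the rest, so the reported half-lives and volumes would come from a selected group. The second is exposure itself at 0.5 µg/kg/min. If the plateau is unquantifiable, the profile is coded 0, its logarithm does not exist, and the log-scale linearity comparison of plasma Cmax and AUC in Protocol 14.2 cannot be run. Section 12 puts 16 of the 24 full-profile patients on this dose.

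**Working it through.** **Inputs**
- Clearance 4500 mL/min at 70 kg; earlier limit 10 ng/mL; parent steady state within one hour and constant afterwards (Protocol 1.2).
- Half-life 10–20 min (Protocol 1.2). It is reported only for rates above 1.66 µg/kg/min, so using it here is an assumption.
- Doses 0.5 and 1.0 µg/kg/min (Protocol 3); 24-hour infusion = 1440 min.

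**Formulas**
- Plateau: Css = rate × weight / clearance.
- Decline: C(t) = Css × 0.5^(t / t½).

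**Plateau at 70 kg**
- 0.5 µg/kg/min: 35 µg/min ÷ 4500 mL/min = 7.8 ng/mL.
- 1.0 µg/kg/min: 70 µg/min ÷ 4500 mL/min = 15.6 ng/mL.
- Per isomer, if E and Z split equally (an assumption): 3.9 and 7.8 ng/mL.

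**The protocol's five-minute observation**
- At 0.5 it agrees: 7.8 is below 10 before the infusion stops.
- At 1.0 it agrees only approximately. The model gives 11.0–13.1 ng/mL at 5 min and reaches 10 ng/mL at 6.4–12.7 min. Falling from 15.6 to below 10 within 5 min needs a half-life under 7.8 min, so the observation suggests a faster fall than the one assumed below.
- Either way, both doses are below 10 ng/mL by the 15-minute sample.

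**Expected total drug after the stop (ng/mL, half-life 10 to 20 min)**

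| Time after stop | 0.5 µg/kg/min | 1.0 µg/kg/min |
|---|---|---|
| 15 min | 2.8–4.6 | 5.5–9.2 |
| 30 min | 0.97–2.75 | 1.9–5.5 |
| 1 h | 0.12–0.97 | 0.24–1.9 |
| 4 h | at most 0.002 | at most 0.004 |

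At a 10 ng/mL limit there are no quantifiable post-infusion points at either dose, against three required. By 4 h, 12 to 24 half-lives have passed, so only three post-infusion samples can inform the parent's decline under any assay.

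**Limit needed for three usable points (total drug)**
- Post-infusion points only (15, 30, 60 min): 0.12–0.97 ng/mL at 0.5; 0.24–1.94 at 1.0.
- Counting the 24-hour end-of-infusion sample (then 15 and 30 min): 0.97–2.75 at 0.5; 1.94–5.5 at 1.0.
- Per isomer, about half of these.

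These ranges also show the selection. With post-infusion points only, at 0.5 and any limit between 0.12 and 0.97 ng/mL, a patient with a 20-minute half-life yields three points and one with a 10-minute half-life yields fewer.

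**Sensitivity at 10 ng/mL**
- At 1.0 with a 20-minute half-life, the 15-minute sample becomes quantifiable if clearance is below about 4160 mL/min, or at 100 kg with clearance still 4500 (13.2 ng/mL). At 100 kg the 30-minute sample is 7.9, so there is one post-infusion point, or two points with the 24-hour sample. That is still short of three.
- At 0.5 the plateau reaches 10 ng/mL if clearance falls to 3500 mL/min, and is 11.1 at 100 kg. The during-infusion statement therefore describes a typical 70 kg patient, not everyone.

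**Size of the tail**
- Area after the stop = Css × t½ / ln 2 = Css × 14.4 to 28.9 min.
- Relative to Css × 1440 min, this is 1.0% to 2.0%.

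**The case against.** A reader might infer that these parameters cannot be obtained at all. The documents do not support that.

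- The 10 ng/mL limit belongs to earlier studies, and the limit of this trial's LC/MS/MS assay is simply not stated.
- The half-life is carried down from higher rates. Section 1.2 itself says pharmacokinetic studies beyond six hours have yet to be done, so the decline after 24 hours is unknown.
- Section 6.3 does not say the three points must follow the stop. Admitting the 24-hour sample relaxes the limit needed.
- Section 6.3 also foresees failure. It qualifies every λz-dependent parameter, requires R² above 0.8 and reports a geometric mean as not calculated when any value is null.
- If the plateau can be measured, the loss in exposure is small, because AUC0-t already captures about 98–99% of the area. The primary endpoint is untouched.

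All of this stands, and it turns the point from an impossibility into a risk. It does not dispose of the point. The feasibility qualifier permits missing values but does nothing about which patients supply the rest. It does not cover Cmax and AUC0-t, and the SAP list omits it for the parent. No document specifies an assay limit that would make the schedule work.

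A reader might also infer that the parent samples could be moved into the first half-hour at no cost. The documents do not support that either. The same six draws in section 12 (seven in section 7) serve PST2915, PST2922 and PST3093, and section 6.3 asks for metabolite λz on the same three-point rule. Moving samples would thin the metabolite profile or add draws.

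**Conclusion.** The point holds as a risk, with medium confidence. At the only quantification limit in the documents, a typical 70 kg patient has no quantifiable post-infusion sample at either dose, and at 0.5 µg/kg/min none during infusion. Parent λz, half-life, AUC0-∞, Cl_T, Cl_R, MRT, V_z and V_ss as defined then fail. They become estimable only if this trial's assay limit is roughly 4 to 80 times lower at 0.5 (10 ÷ 2.75 = 3.6; 10 ÷ 0.12 = 83), depending on the half-life and on whether the 24-hour sample counts.

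The conclusion rests on the stated clearance, a 10–20 minute half-life extrapolated to lower rates, single-exponential decline and, for the isomer figures, an equal E/Z split. The defect is a schedule and a set of definitions not reconciled with section 1.2, together with an unstated assay limit.

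**What to change.** 1. **Protocol 6.3, repeated in the SAP.** Calculate parent clearance as infusion rate divided by the mean plateau concentration at 3, 6, 12 and 24 hours, with the 24-hour sample drawn before the pump stops. Calculate Cl_R with AUC0-t. Neither needs λz, the omitted tail is about 1–2% of the area, and the samples are already drawn. The cost is wording only.
2. **Protocol 12 and 6.3.** State the LC/MS/MS quantification limit. Confirm before the first PK patient that it lies well below the expected per-isomer plateau at 0.5 µg/kg/min, about 3.9 ng/mL. Do not enter post-dose values below the limit as 0 in the log-scale linearity analysis. The cost is an assay specification and one sentence of handling rules. Item 1 works at 0.5 only if this condition is met.
3. **Protocol 7 and 12.** Reconcile the post-infusion sampling times with section 1.2 and with each other, since section 7 lists a 48-hour sample that section 12 omits. If parent samples are moved earlier, state openly what the metabolite profile loses or how many draws are added.
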